8.1.7 Area Under the Curve

For PCS total score, the 3 domains of PCS and the 5 domains of the CSQ, the Area under the curve (AUC), for each score over time, will be calculated from baseline to last follow-up visit.

As patients will not be on the study for the same length of time, AUC will then be adjusted by the duration which each patient is in the trial, where duration is calculated as per Section **Error! Reference source not found..**

Thus, adjusted AUC will be calculated as:

$$\frac{\text{Area under the Curve}}{\text{Duration of time on study}}$$

8.2 STATISTICAL ANALYSES

All analyses will be performed in the statistical software SAS 9.3 (or higher), unless otherwise specified.

8.2.1 Background, Demographic Characteristics and Study Disposition

The demographic and baseline summaries will use the Full Analysis Set (FAS). Continuous variables will be summarised as per Section **Error! Reference source not**

found., the categorical variables will be summarised as per Section 8.1.5 and the binary variables will be summarised as per Section **Error! Reference source not found..**

These summaries will include age, sex, height, weight, smoking status, severity of disease, duration of disease, anti-citrullinated protein antibodies (ACPA), rheumatoid factor (RF), vaccination status, presence of poor prognostic factors, comorbidities, co-medication and concomitant medication.

The number and percentage of patients at each time point, described in **Table 9** in Section 11.1, will be provided along with reasons for withdrawal from the study. For patients who have discontinued Tofacitinib treatment but remain in the study information on the treatments prescribed following study treatment (Tofacitinib) will be listed.

8.2.2 Safety Analyses

All safety analyses will use the Safety Analysis Set. All safety analyses will present a single Tofacitinib Total column using the treatment label seen in Section 2.3.

8.2.2.1 Adverse Events

Adverse events (AE's) will be summarized according to Pfizer standards, presenting AE's, Serious AE's and non-serious AE's.

Two sets of AE's will be summarised as 'All Casualty' and 'Treatment Emergent'. For the treatment emergence table, a drug lag of 28 days will be applied following cessation of Tofacitinib.

The AE listings will list the individual drugs that were being taken at the time of the AE.

Adverse events which occurred under another DMARD, following cessation of Tofacitinib, will be presented in separate listing. Note: A drug lag of 0 days will be applied following the cessation of Tofacitinib, for AE's occurring under another DMARD, e.g. if an AE is within 28 days of Tofacitinib and started after the cessation of Tofacitinib then it will be seen within both listings (for Treatment-Emergent and occurred under another DMARD following cessation of Tofacitinib).

8.2.2.2 Exposure Data

[figure not shown]
Exposure data will be summarised including dose, dose change and reason for change.

8.2.3 Primary Analyses

The primary endpoint, duration of Tofacitinib drug survival, will be analysed using the FAS and the methods described in Section 8.1.1.1 Cox Proportional Hazards. The Tofacitinib drug survival tables will present a single Tofacitinib Total column, using the treatment label seen in Section 2.3. A Kaplan-Meier plot will present the survival function for Tofacitinib Total group. As a comparison, a second KM plot will present the

survival functions for both Tofacitinib as Monotherapy and Tofacitinib as Combination groups. The treatment labels seen in Section 2.3 will be used.

The list of potential predictive factors to include in the model for the primary analysis is seen in [Figure 2](#). Note: the factors seen in Figure 2 are all baseline predictors. Where SF-12 is considered within [Figure 2](#), the 8 health domains as well as PCS_{SF12} and MCS will each be considered as potential predictive factors. As PCS_{SF12} and MCS are linear combinations of the 8 health domains, collinearities are anticipated, however considering all of them as potential predictors will allow us to investigate which domains contribute the most to PCS_{SF12} and/or MCS. If necessary, transitional models will be investigated including separately component summary measures (PCS_{SF12} and MCS) and the 8 health domains.

Figure 2: Potential predictive factors of drug survival

In the event of missing data, see Section 7.1. Missing data methods will be performed on the final multivariate Cox PH model, and not for the individual univariate models.

8.2.4 Sensitivity Analyses

Sensitivity analyses, except where specified, will use the FAS. All sensitivity analyses tables will present a single Tofacitinib Total column, using the treatment label seen in Section 2.3. All sensitivity analyses plots will present Tofacitinib as Monotherapy and Tofacitinib as Combination, using the treatment labels seen in Section 2.3.

Complete Case Analysis

In the event of more than 10% missing data in baseline covariates then a complete case analysis will take place, using the methods described in Section 7.2.

Random Survival Forests

Random survival forests will be created as a sensitivity analysis to complement the standard Cox PH model, as described in Section 8.1.1.2 Random Survival Forests, and will consider the potential predictive factors seen in Figure 2 in Section 8.2.3. In the event of missing data, see Section 7.3.

DAS28-4 CRP at Month 3 as a Potential Predictive Factor

8.2.5 As part of the sensitivity analyses, DAS28-4 CRP at month 3 will be considered as an additional potential predictive factor along with the factors seen in Figure 2 in Section 8.2.3, and will follow the methods described in Section Analysis of 8.1.1.1 Cox Proportional Hazards. This will use the Month 3 Analysis Set. In the event of missing data, follow Section 7.1.

The methods for random survival forests, described in Section 8.1.1.2 Random Survival Forests, will also be repeated including DAS28-4 CRP at month 3 as a potential predictive factor, along with the factors in Figure 2 in Section 8.2.3. This will use the Month 3 Analysis Set. In the event of missing data, follow Section 7.3.

8.2.6 Secondary Analyses

All secondary analyses will use the FAS. Secondary analyses will consider Tofacitinib Total as the treatment group. Summaries of secondary endpoints will be presented for Tofacitinib total, Tofacitinib as monotherapy and Tofacitinib as combination, using the treatment labels seen in Section 2.3.

Each endpoint will apply the specific rules for missing data as described in Section 7 but if there are missing data points after this, no missing data methods will be used to impute data for the secondary analyses.

All the analyses described hereafter in this section will be performed on all assessments collected before permanent Tofacitinib discontinuation (On-Treatment Analysis). In addition, analyses described in sub-sections 8.2.6.2, 8.2.6.3, 8.2.6.4 and 8.2.6.5 will be re-run on all available data including retrieved dropout data (Analysis on All Available Data).

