9. METHODS

9.1. Study design

9.1.1. Study Schema

This is an observational, open-label, prospective, multi-centre, national study designed to identify factors predictive of Tofacitinib’s survival in patients with RA. Additionally it will provide real world patient outcome in France. Furthermore, data from France will be compared and also pooled with data from other countries. Details will be included in a separate analysis plan for a pooled analysis.

Figure 1: Study schema

Patients can be enrolled in the study by their rheumatologist if they satisfy all of the following criteria for inclusion. All visits must be scheduled according to usual clinical practice. Medical follow-up of patients is independent of enrolment of patients in the study.

In the setting of this study, 6 visits can be documented. Data will be collected from the patient's medical dossier at V0 and at time of the 6 follow-up visits: at 1 month (V1), at 3 months (V2), at 6 months (V3), at 12 months (V4), at 18 months (V5) and at 24 months (V6). No sample will be collected specifically for this study. At each visit, patients will be subjected to management in compliance with healthcare standards. In order to collect comparable study data, visits 2 to 6 performed within ± 14 days after planned date of the visit will be used for analysis of data.

In case of discontinuation of treatment with Tofacitinib, for whatever reason, clinical data will be collected as close as possible to the date of such a discontinuation.

Likewise, in case of Tofacitinib discontinuation outside the 6 scheduled visits, an additional visit to collect clinical data as close as possible to the date of this discontinuation should be organised.

Eligible patients will be followed starting from the date of the first prescription of Tofacitinib during 24 months, whether they continue treatment with Tofacitinib or not.

The dose and duration of treatment, as well as the frequency of follow-up of the patient must be based on clinical and individual needs and will be determined by the rheumatologist. To provide precise information on treatment, the initial dose of Tofacitinib and all changes and reasons for changes will be documented in the evaluation.

All AE spontaneously reported by the patient or observed by the participating physician during the study will be recorded on the AE page of the electronic case report form (eCRF).

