2.2 STUDY POPULATION

Patients eligible for this study can be included by the physician if they are starting a treatment with Tofacitinib for RA according to usual clinical practice and satisfy all of the criteria for inclusion. Patient treatment is independent from patient enrolment into the study.

Data will be recorded during the 24 months participation of each patient. Visits, target dates and windowing is described in [Table 9](#), Section [11.1](#).

Patients will be followed prospectively and follow-up visits will be conducted after the initial consultations. No visit or additional test is required by the protocol, since the study is observational: the modalities for follow-up and treatment will be left up to the sole judgement of the participating doctor.

In case of discontinuation of treatment with Tofacitinib, for whatever reason, clinical data will be collected as close as possible to the date of such a discontinuation. Likewise, in case of Tofacitinib discontinuation outside the 6 scheduled visits, an additional visit to collect clinical data as close as possible to the date of this discontinuation should be organised.

Eligible patients will be followed starting from the date of the first prescription of Tofacitinib during 24 months, whether they continue treatment with Tofacitinib or not.

In order to ensure expected recruitment, the study will be conducted by about 100 rheumatologists. Participating physicians will be selected from among those all over France out of the total number of French health institutions which manage patients with rheumatoid arthritis.

In order to reach an objective of participation of 100 centres desired, the study will be offered to about 550 centres.

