6.1.1.2.1 PCS – Pain Catastrophising Scale

The Pain Catastrophising Scale (PCS) is a 13 item questionnaire around thoughts and emotions experienced during pain, with each question on a 5 point scale (0 = 'Not at all' to 4 = 'All the time'). There are three subscales of PCS: Rumination (thinking deeply), exaggeration and helplessness. [Table 2](#) shows an overview of the items which belong to each domain.

Table 2 Overview of Domains for PCS ([5](#))

Domain	Items
Rumination	8, 9, 10, 11
Exaggeration	6, 7, 13
Helplessness	1, 2, 3, 4, 5, 12

Total scores and domain scores are derived by summing the scores of the individual items. The highest possible score of PCS is 52, and a total score of ≥ 20 indicates a clinically relevant level of catastrophisation. PCS will be considered both in terms of individual domain scores and total scores. PCS total score will be analysed as a continuous variable as well as a dichotomous variable (<20 vs ≥ 20).

For the handling of missing data when deriving PCS scores, see Section [7.4](#).

PCS is collected at all visits (Inclusion visit, V1, V2, V3, V4, V5, V6 and any additional visits in the case of discontinuation of Tofacitinib).

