6.1.1.2.2 CSQ – Coping Strategies Questionnaire

The Coping Strategies Questionnaire (CSQ) evaluates cognitive coping and, in its French version, is split into 5 domains: “Distraction”, “Catastrophising”, “Distancing from Pain”, “Ignoring Pain Sensations” and “Praying”. The CSQ consists of 21 items in total and for each item, subjects rate the frequency of their use of each coping strategy on a 4-point Likert-type scale. CSQ is collected on the CRF as the following: 1: Never, 2: Sometimes, 3: Often and 4: Very often. In order to consider values comparable to the standard CSQ French Version, the following mapping will be done.

CSQ Text Value	CRF Value	Map to standard value
Never	1	0
Sometimes	2	1
Often	3	2
Very Often	4	3

This endpoint is considered in terms of the 5 domains, and a total score is not considered for CSQ. Domain scores are derived by summing the individual items scores that make-up the domain. Details of the 5 domains are provided below.

Domain	Items as numbered on CRF	Domain Score Range
Distraction	2, 10, 11, 19, 20	0 – 15
Catastrophising	3, 9, 15, 18	0 -12
Distancing from Pain	1, 5, 13, 21	0 – 12
Ignoring Pain Sensations	6, 7, 8, 14, 16	0 – 15
Praying	4, 12, 17	0 - 9

CSQ is collected at all visits (Inclusion visit, V1, V2, V3, V4, V5, V6 and any additional visits in the case of discontinuation of Tofacitinib).

For the handling of missing CSQ data, see Section [7.5](#).

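### SAP 8.2.6 leaves only the PCS/CSQ section (8.2.6.1) out of the all-available-data re-run, so PCS/CSQ values after stopping, and on the stop date if read strictly, miss the by-visit summaries, Figure 3 and Figure 4

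*SAP*

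**What the plan says.** Protocol 9.1.1 asks for clinical data around the time of stopping. If the stop falls between scheduled visits, "an additional visit to collect clinical data as close as possible to the date of this discontinuation should be organised". Follow-up continues "during 24 months, whether they continue treatment with Tofacitinib or not" (SAP 2.2).

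Both behavioural questionnaires are completed at that visit. SAP 6.1.1.2.1 lists for PCS "any additional visits in the case of discontinuation of Tofacitinib", and SAP 6.1.1.2.2 has the same provision for CSQ. Change from baseline in PCS and in CSQ are the first two secondary endpoints in Protocol 9.1.6.2. Their correlation with effectiveness is a secondary objective (Protocol 8), and Protocol 9.7 sets no on-treatment limit on it.

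SAP 8.2.6 sets the data cut for everything in the section: the analyses "will be performed on all assessments collected before permanent Tofacitinib discontinuation (On-Treatment Analysis". It then adds that "analyses described in sub-sections 8.2.6.2, 8.2.6.3, 8.2.6.4 and 8.2.6.5 will be re-run on all available data including retrieved dropout data". Section 8.2.6.1 is not on that list, and no reason is given.

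**The concern.** Section 8.2.6.1 holds the PCS and CSQ summaries, the Figure 3 correlations with effectiveness, the Figure 4 logistic models and three Cox models. Because it is the only part of 8.2.6 with no second analysis, whatever the on-treatment cut removes from the by-visit outputs is not put back.

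The cut is also not fully defined. The SAP does not say whether an assessment made on the stop date counts as *before* discontinuation. That matters, because a visit at which the physician stops the drug carries exactly that date.

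At stake is how the change in catastrophising and coping, and its relation to effectiveness, is described in patients who stop. If their state at stopping is left out, the by-visit results lean towards patients who stay on the drug. The data have been collected at some effort, and the gap covers all PCS/CSQ values after stopping, not just those from the discontinuation visit.

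**Working it through.** **The plan's own figure.** Protocol 9.5 assumes 50 candidate factors, 30% passing the univariate screen, 10 events per variable and 50% drug survival at 24 months. Events = 50 × 0.3 × 10 = 150, and N = 150 / 0.50 = 300. Both match the protocol. So about 150 of 300 patients are expected to stop.

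**What each part of 8.2.6 receives.**

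| SAP section | Content | On-treatment | All available data |
|---|---|---|---|
| 8.2.6.1 | PCS/CSQ summaries, correlations, logistic and Cox models | yes | no |
| 8.2.6.2 | DAS28, joint counts, stiffness, EQ-5D, SF-12, FACIT-Fatigue, pain | yes | yes |
| 8.2.6.3 | EULAR response, GIRERD | yes | yes |
| 8.2.6.4 | LDA, remission, FiRST | yes | yes |
| 8.2.6.5 | SDAI, CDAI, PhGA, PtGA, Boolean criteria, baseline PCS model | yes | yes |

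The only PCS analysis in a repeated section (8.2.6.5) uses baseline PCS, so it brings in nothing from after baseline.

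**Where the discontinuation visit can fall.** Before the stop date, it is kept. On the stop date, its status is undefined, and it is lost on a strict reading. After the stop date, it is lost.

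**Number at stake.** Let f be the share of discontinuation visits held after the stop date, or on it under the strict reading. The excluded PCS/CSQ stop assessments are 150 × f:

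- f = 0: 0
- f = 25%: 37.5
- f = 50%: 75
- f = 75%: 112.5
- f = 100%: 150

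The documents give no value for f. SAP 2.1 still states 500 patients. At 50% survival that would be 250 stops, which changes the scale but not the point.

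**Which outputs the stops could reach.** Assume a constant hazard, S(t) = exp(−t × ln 2 / 731). Expected stops in a Table 9 window from day a to day b are 300 × [S(a−1) − S(b)]:

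- V1 16.6, M3 19.7, M6 32.1, M12 36.9, M18 30.8, M24 13.7 (to day 731); total 149.7
- Windows used by Figures 3 and 4 (M3, M6, M12, M24): 19.7 + 32.1 + 36.9 + 13.7 = 102.4
- V1 and M18, which those figures never use: 16.6 + 30.8 = 47.4

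**Effect of the one-value-per-window rule.** Table 9 keeps the observation closest to the target day. A stop-date assessment is the only on-treatment value in its window mainly when the stop precedes the target day. If every stopper is seen on the stop date, that is 300 × [S(window start) − S(target day)]: M3 7.7, M6 11.0, M12 18.9, M24 13.5, about 51 in all. When the stop follows the target day, a scheduled visit held near that day is usually closer and is used instead. In an all-data re-run, a later visit can also displace the stop visit: for a stop on day 300 and a month-12 visit on day 365, the day-365 value is used.

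**The case against.** Several points on the other side stand.

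- **The discontinuation visit is not discarded outright.** A reader of the on-treatment sentence alone might infer that it is, and that on-treatment LDA and remission are flattered with no check. The next sentence of SAP 8.2.6 sends the effectiveness endpoints into the all-available-data re-run, so the documents do not support that reading.
- **PCS/CSQ at stopping are not absent from every output.** The AUC in SAP 8.1.7 runs to the last follow-up visit and feeds a correlation in 8.2.6.1. Patients without the adverse event of interest are summarised on their last measurement in the study. SAP 8.2.7 states no on-treatment limit. The first two, however, conflict with the limit in 8.2.6, which covers all analyses in that section.
- ***Before* can be read inclusively.** An assessment at which the physician then decides to stop was arguably made before stopping. SAP 6.1.1.1 adds one day to stop date minus start date, which counts the stop date as a day on drug. This is a fair reading, but the SAP does not state it, and it does nothing for visits after the stop date.
- **The Cox models are right as they are.** A predictor of discontinuation should be measured before the event.
- **The analyses are secondary, and SAP 4 states no formal hypotheses.** That limits the consequence. It does not explain why one section is treated differently from the other four.

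**Conclusion.** The concern holds in a limited form. PCS/CSQ values taken after the stop date, and on it under a strict reading, are outside the by-visit summaries, the Figure 3 correlations and the Figure 4 logistic models, with no second analysis to bring them in. Effectiveness endpoints do not share this gap.

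The size is between 0 and about 150 stop assessments among 300 patients. It rests on the protocol's 50% survival assumption and on a timing share that the documents do not give. A reader might infer that all 150 stoppers lose their end-of-treatment assessment. That needs every discontinuation visit to fall on or after the stop date and every same-day value to be excluded, so it is an upper bound. About 102 of the expected stops lie in windows that Figures 3 and 4 use, given a constant hazard. No effect on the PCS or CSQ estimates can be calculated, because the documents give no values for patients who stop.

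**What to change.** 1. In SAP 8.2.6, define on-treatment as assessments up to and including the date of permanent discontinuation.
2. Add the 8.2.6.1 summaries, correlations and logistic models to the all-available-data re-run. State that the Cox models keep using values from before discontinuation, so that step 1 does not alter them.
3. Reconcile the on-treatment limit with the AUC to last follow-up visit (8.1.7) and the last-measurement-in-study summary (8.2.6.1), and say whether it applies to 8.2.7.

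Extending the on-treatment period by the 28-day lag of SAP 8.2.2.1 is not advised. That lag assigns adverse events, and nothing in the documents supports it for questionnaire or efficacy scores.

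The cost is SAP wording and one more set of tables, with no new data. The re-run will include values taken after patients switch treatment and should be labelled accordingly. Because of the Table 9 rule, the changes lessen the loss of stop-visit values but do not remove it.

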8.2.6.1 Behavioural Strategies – PCS and CSQ

The impact of behavioural strategies (PCS total score and 5 domains of the CSQ) on Tofacitinib drug survival will be analysed, using three multivariate Cox PH models as described in Section 8.1.1.1 Cox Proportional Hazards.

PCS (individual domain scores and total scores) and CSQ (individual domain scores) will also be summarised as continuous variables as per Section **Error! Reference source not found.** PCS total score will also be summarised as a dichotomous variable (<20 vs ≥ 20) as per Section **Error! Reference source not found.**

Correlations between the behavioural strategies (PCS total score and 5 domains of the CSQ) and each of the endpoints listed below will be investigated as outlined in Section **Error! Reference source not found.**, for the endpoints seen in Figure 3:

- DAS28-4 ESR
- DAS28-4 CRP
- TJC
- SJC
- Duration of morning stiffness
- GIRERD Questionnaire
- EuroQoL EQ-5D-3L
- SF-12v2 Questionnaire
- FACIT-Fatigue Questionnaire
- DAS28 (EULAR Criteria)
- Pain

Figure 3 Timepoints for correlation analyses

Behavioural Strategies Timepoint	Effectiveness Endpoint Timepoint
M0 (Baseline)	M3
M0 (Baseline)	CFB to M3 (M3-M0)
M3	M3
M3	CFB to M3 (M3-M0)
CFB to M3 (M3-M0)	M3
CFB to M3 (M3-M0)	CFB to M3 (M3-M0)
M0 (Baseline)	M6
M0 (Baseline)	CFB to M6 (M6-M0)
M6	M6
M6	CFB to M6 (M6-M0)
CFB to M6 (M6-M0)	M6
CFB to M6 (M6-M0)	CFB to M6 (M6-M0)
M0 (Baseline)	M12
M0 (Baseline)	CFB to M12 (M12-M0)
M12	M12
M12	CFB to M12 (M12-M0)
CFB to M12 (M12-M0)	M12
CFB to M12 (M12-M0)	CFB to M12 (M12-M0)
M0 (Baseline)	M24
M0 (Baseline)	CFB to M24 (M24-M0)
M24	M24
M24	CFB to M24 (M24-M0)
CFB to M24 (M24-M0)	M24
CFB to M24 (M24-M0)	CFB to M24 (M24-M0)

M = Month. CFB = Change from baseline.

Logistic regression will be considered to assess the relationship between behavioural strategies (PCS total score and 5 domains of the CSQ) and each of the binary endpoints listed below as outlined in Section **Error! Reference source not found.**, with a separate model created for each of the timepoints seen in Figure 4:

- LDA
- Patients in remission
- FiRST Questionnaire

Figure 4 Timepoints for logistic regression

Behavioural Strategies Timepoint	Effectiveness Endpoint Timepoint
M0 (Baseline)	M3
M3	M3
CFB to M3 (M3–M0)	M3
M0 (Baseline)	M6
M6	M6
CFB to M6 (M6–M0)	M6
M0 (Baseline)	M12
M12	M12
CFB to M12 (M12–M0)	M12
M0 (Baseline)	M24
M24	M24
CFB to M24 (M24–M0)	M24

M = Month. CFB = Change from baseline.

Further summaries will be produced to investigate the relationship between behavioural strategies and the adverse event (AE) groups Herpes Zoster and Serious Infections. Serious infections are as defined in Section 6.2. The summaries will be presented separately for the two groups, and are as follows:

- The baseline behavioural strategies (PCS total score, PCS (3 domains) and CSQ (5 domains)) statistics, summarized as per Section **Error! Reference source not found.**, will be presented for patients who experienced each AE of interest (Herpes Zoster/Serious Infection) and for patients who did not experience the AE of interest.
- The last behavioural strategies (PCS total score, PCS (3 domains) and CSQ (5 domains)) statistics, summarized as per Section **Error! Reference source not found.**, for measurements prior to the first occurrence of the AE of interest (for patients who experienced the AE of interest) will be presented. The last behavioural strategies measurements in the study for patients who did not experience the AE of interest will also be presented.
- Correlation between the number of AE's of interest and behavioural strategies (PCS total score, PCS (3 domains) and CSQ (5 domains)) at baseline will be

examined using the methods described in Section **Error! Reference source not found..**

- Correlation between the number of AE's of interest and the last behavioural strategies (PCS total score, PCS (3 domains) and CSQ (5 domains)) prior to the first occurrence of an AE will be examined using the methods described in Section **Error! Reference source not found..**
- The correlation between the adjusted number of AE's (see Section 6.2) and the adjusted AUC for PCS and CSQ (see Section **Error! Reference source not found..**) will be calculated and presented, as per Section **Error! Reference source not found..** This will be done for:
 - PCS total score.
 - The 3 domains of the PCS.
 - The 5 domains of the CSQ.
- The change in behavioural strategies (PCS total score, PCS (3 domains) and CSQ (5 domains)) before and after start of the first occurrence of the AE of interest will be presented for the subset of patients who experience the AE of interest, summarized as per Section **Error! Reference source not found..**

